7.2 Drug Information on G-CSF (Granulocyte colony-stimulating factor)

- 7.2.1 Mechanism of Action: G-CSF is a growth factor that stimulates the production, maturation, and activation of neutrophils. Further, it promotes premature release of neutrophils from the bone marrow and enhances their phagocytic capacity.
- 7.2.2 Pharmacokinetics: Peak G-CSF concentrations after sub-cutaneous dosing occur in 2 to 8 hours, though the onset of action is approximately 24 hours, with plateau concentrations in 3-5 days, and elimination over an 11-20 day period. G-CSF is cleared by systemic degradation. Notably, as G-CSF binds neutrophils, plasma levels are controlled in large part by the absolute neutrophil count.[29]
- **7.2.3** Adverse Effects (AEs): Common drug-related AEs (occurring in >10% of patients) include fever, petechiae, elevated uric acid, splenomegaly, bone pain, and epistaxis. Less common drug-related AEs (occurring in 1% -10% of patients) include hyper- or hypotension, arrhythmias, headache, nausea, vomiting, leukocytosis, and transfusion reaction. Infrequent drug-related AEs (occurring in <1% of patients) include acute respiratory distress syndrome, allergic reactions, alopecia, alveolar hemorrhage, arthralgia, bone density decrease, capillary leak syndrome, cerebral hemorrhage, vasculitis, dyspnea, edema, erythema nodosum, hematuria, hemoptysis, hepatomegaly, hypersensitivity, injection site reaction, pericarditis, proteinuria, psoriasis exacerbation, pulmonary infiltrates, renal insufficiency, sickle cell crisis, splenic rupture, Sweet's syndrome, tachycardia, and thrombophlebitis.
- 7.2.4 Recommended dose adjustments for organ dysfunction: There is limited or no data examining the toxicity of G-CSF in patients with renal or liver dysfunction. Therefore, administration of G-CSF to patients with liver or kidney disease must be done with caution.

7.3 Drug Information on Cladribine (2-chloro-2'-deoxyadenosnie, 2-CdA)

- 7.3.1 Mechanism of Action: Cladribine is a prodrug that is converted to an adenosine deaminase-resistant triphosphate derivative (2-CdATP). This molecule is then activated by deoxycytidine kinase to a 5'-triphosphate derivative (2-CdAMP), which is incorporated into DNA where it acts as a transcription regulator. In addition to its cytotoxic properties in dividing cells, cladribine induces death in quiescent cells of lymphoid origin through an unknown mechanism.[30]
- 7.3.2 Pharmacokinetics: Cladribine is renally excreted, with 18-35% as unchanged drug. It is able to penetrate the CSF, where it achieves 25% of plasma concentrations. It is 20% protein-bound. The half-life for elimination after a 2-hour infusion is 6.7±2.5 hours in patients with normal renal function.
- 7.3.3 Adverse Effects: Common adverse effects (occurring in >10% of patients) include fever, fatigue, headache, rash, nausea, anorexia, vomiting, myelosuppression (including grade 3/4 neutropenia/thrombocytopenia), injection site reaction, and infection. Less common adverse effects (occurring in 1 to 10% of patients) include edema, tachycardia, thrombosis, chills, dizziness, insomnia, malaise, diarrhea or constipation, weakness, myalgias and arthralgias, cough, dyspnea, epistaxis, and diaphoresis. Rare adverse effects (occurring in <1% of patients) include aplastic anemia, bacteremia, opportunistic infections, lymphocytopenia,

altered mental status, hemolytic anemia, hypersensitivity, myelodysplastic syndrome, quadriparesis, and renal dysfunction/failure.

- 7.3.4 Reconstitution: Cladribine is supplied as a sterile, preservative-free, isotonic solution containing 10 mg of cladribine (1 mg/mL) in 10 mL single-use vials. Cladribine should be passed through a sterile 0.22µm filter prior to introduction into the infusion bag containing 0.9% Sodium Chloride Injection, USP.
- **7.3.5** Administration and Compatibility: The use of 5% dextrose is not recommended as a diluent because of increased degradation of cladribine. The infusion solution is stable for 24 hours at room temperature.
- **7.3.6** Storage and Stability: Store refrigerated 2° to 8°C (36° to 46°F). Protect from light during storage.
- **7.3.7** Recommended Dose Adjustments for Organ Dysfunction: Specific guidelines for cladribine dosing in patients with hepatic/renal dysfunction or hypoalbuminemia are not clearly defined. Because of the potential for compensatory elimination of cladribine in patients with hepatic and/or renal dysfunction, specific guidelines for dosing are difficult to define. Thus, when deciding whether to adjust cladribine doses for renal dysfunction, the risks for potential toxicities (e.g., myelosuppression, neurotoxicity) against the benefits and goals of treatment must be considered.

7.4 Drug Information on Cytarabine (Cytosine arabinoside)

- 7.4.1 Mechanism of Action: Cytarabine is a synthetic pyrimidine analog, in which the sugar moiety (normally a ribose or deoxyribose) has been replaced with arabionose. Although its mechanism of action is not completely understood, the active form of cytarabine is probably incorporated into the DNA and interferes with DNA synthesis. As such, cytarabine has been found to primarily effect dividing cells, blocking their progression from G_1 to S phase [31, 32].
- 7.4.2 Human Pharmacokinetics: Cytarabine is metabolized by deoxycytidine kinase and other kinases into its most active form (aracytidine triphosphate). Aracytidine triphosphate is converted to nontoxic uracil derivatives by pyrimidine nucleoside deaminases. This balance between the levels of kinases and deaminases is critical for regulating the sensitivity/resistance of cells to the drug. Like decitabine, the plasma clearance of cytarabine is biphasic: initial rapid phase and more prolonged second clearance phase. The rapid clearance phase has a relatively short half-life $(t_{1/2\alpha} = 10 \text{ minutes})$, while the half-life of the second clearance phase is slightly longer $(t_{1/2\beta} = 1 3 \text{ hours})$. The nontoxic metabolites from the drug are excreted in the urine, and within 24 hours after the infusion, approximately 80% of these nontoxic metabolites can be recovered from the urine [31, 32].
- 7.4.3 Human Toxicology and AEs Associated with Standard Doses of Cytarabine: The dose-limiting toxicity for cytarabine includes myelosuppression and cardiotoxicity. Cumulative doses beyond 550 mg/m² result in increased risk for congestive heart failure. *Frequent AEs (not definitely quantified)* include the following: myelosuppressionleucopenia, anemia, neutropenia, thrombocytopenia and related bleeding, pyrexia, rash, anorexia, diarrhea, nausea, vomiting,

mucositis, anal inflammation or ulceration, hepatic dysfunction or increased liver enzymes, and local thrombophlebitis. Less frequent AEs (not definitely quantified) include chest pain, pericarditis, dyspnea dizziness, headache, neural toxicity, neuritis, alopecia, pruritis, skin freckling, skin ulceration, urticaria, abdominal pain, bowel necrosis, esophageal ulceration, esophagitis, pancreatitis, sore throat, urinary retention, jaundice/hyperbilirubinemia, local site cellulites, renal dysfunction, allergic edema or anaphylaxis, sepsis, and sudden respiratory distress syndrome. Infrequent AEs (not definitely quantified) include aseptic meningitis, cardiopulmonary arrest, cerebral dysfunction, cytarabine syndrome (bone pain, chest pain, conjunctivitis, fever, maculopapular rash, malaise, myalgia), exanthematous pustulosis, hyperuricemia, intestinal pneumonitis, increased lipase, paralysis with intrathecal and IV combination therapy, rhabdomyolysis, venoocclusive disorder, and death. Adverse Events Associated with High Dose Cytarabine include cardiomegaly and cardiomyopathy, coma. severe neurotoxicity, personality change, somnolence, total body alopecia, severe rash or skin desquamation, gastrointestinal ulceration, peritonitis, intestinal pneumatosis, necrotizing colitis, liver abscess or damage, peripheral neuropathy, corneal toxicity, hemorrhagic conjunctivitis, pulmonary edema, sudden respiratory distress syndrome, and sepsis [31, 32].

- 7.4.4 Reconstitution: Cytarabine should be reconstituted in sterile water and can be further diluted using either 5% dextrose or sodium chloride solutions into appropriate concentrations for infusion [31, 32].
- 7.4.5 Administration and Compatibility: The diluted cytarabine solution should be inspected for particulate matter, discoloration, and haze prior to infusion. If there is evidence of particulate matter, discoloration, or haze the solution should not be infused. Patients should be medicated with standard anti-emetic therapy. Cytarabine is not compatible (1) during Y-site administration with allopurinol, amphotericin B, ganciclovir; (2) in syringe with metoclopropamide; or (3) admixed with fluorouracil, heparin, insulin (regular), nafcillin, oxacillin, penicillin G. Cytarabine may have variable compatibility when admixed with gentamycin, hydrocortisone, and methylpredinsone [31, 32].
- **7.4.6** Storage and Stability: Vials of non-reconstituted cytarabine should be stored at room temperature 15°C 30°C (59°F 86°F). The diluted cytarabine solution may be stable for up to 48 hours if stored at room temperature [31, 32].
- 7.4.7 Drug-Drug Interaction: Reversible decreases in the plasma steady-state concentration for digoxin and cardiac glycosides may occur. Cytarabine may diminish the therapeutic effect of flucytosine. There is *ex vivo* data suggesting that cytarabine may reduce the effectiveness gentamycin for killing *K. pneumoniae*.
- 7.4.8 Warnings and Precautions: *Ex vivo* and *in vivo* studies have found that cytarabine causes extensive chromosomal damage and potential malignant transformation. Although there have been some case reports describing cytarabine use in pregnant humans, these cases reports are few. Thus, cytarabine is considered Pregnancy Category D. Women should be advised not to become pregnant while receiving cytarabine, and men should be advised not to father a child while receiving

cytarabine and for at least 3 months after completing the therapy. It is not known whether cytarabine or its metabolites are excreted in breast milk; thus, it is not recommended for lactating females who are breast-feeding. As with any highly immunosuppressive medication, cytarabine may diminish the effectiveness of dead and live vaccines and enhance the toxic/adverse effect of live vaccines. One should avoid use of live vaccines while receiving it. A small percentage of patients will have a hypersensitivity reaction to cytarabine, and these individuals should not receive the drug again.

7.4.9 Recommended Dose Adjustments for Organ Dysfunction: Guidelines for adjusting cytarabine dose due to renal or liver dysfunction are not standardized, but many clinicians will adjust the dose based upon the function of these organs.

7.5 Drug Information on Mitoxantrone

- 7.5.1 Chemistry: Mitoxantrone (dihydroxyanthracenedione) is an anthracenedione derivative that intercalates with DNA, resulting in inhibition of nucleic acid synthesis.
- 7.5.2 Pharmacokinetics: A three-compartment model was described after a single intravenous dose of mitoxantrone. The mean alpha half-life is 6 to 12 minutes, the mean beta half-life is 1.1 to 3.1 hours, and the mean terminal (gamma) or elimination half-life is 23 to 215 hours (median 75 hours). Mitoxantrone has extensive distribution into body tissues and is metabolized in the liver to two main inactive metabolites (monocarboxylic acid derivative and dicarboxylic acid derivative). The major route of excretion for mitoxantrone appears to be biliary into the feces; approximately 11% of the dose is recovered in the urine within 5 days of drug administration, with 65% of this being unchanged drug.
- **7.5.3** Adverse Effects: The most common toxicities associated with mitoxantrone are alopecia, nausea/vomiting, Mitoxantrone will cause cardiac toxicity with prolonged administration and doses exceeding 80 to 100 mg/m². When used after doxorubicin, cardiotoxicity is more frequent; an analysis by the Southwest Oncology Group revealed a risk of 6% at 134 mg/m² prior doxorubicin and 60 mg/m² mitoxantrone, rising to a 15% risk at 120 mg/m² mitoxantrone. Cardiac events reported included arrhythmias, decreased left ventricular function, chronic heart failure, tachycardia, ECG changes, and, infrequently, myocardial infarction. Bradycardia has been rarely reported. Patients with prior treatment with anthracyclines, prior mediastinal radiotherapy, or with preexisting cardiovascular disease may have more frequent occurrences of cardiac toxicity.

8.0 EVALUATION AND END POINT DEFINITIONS

8.1 Treatment Response and Outcome

Treatment response (e.g. morphologic / cytogenetic / molecular complete remission, partial remission) or treatment failure (e.g. resistant disease, aplasia, morphological or molecular / cytogenetic relapse) as well as treatment outcome (e.g. overall survival, relapse-free survival, event-free survival, and remission duration) are categorized according to criteria recommended by International Working Groups [21, 33]. Patients are routinely assessed for the presence of

measurable residual disease (MRD) as detected by multiparameter flow cytometry, as per institutional practice.

8.2 Toxicity Criteria

This study will use the CTCAE (NCI Common Terminology Criteria for Adverse Events) Version 4.0 for Toxicity and Adverse Event reporting. A copy of the CTCAE v4.0 can be downloaded from the CTEP home page (http://ctep.cancer.gov).

8.3 Definition of Dose-limiting Toxicities (DLTs)

Reported adverse events and potential risks for decitabince, G-CSF, cladribine, cytarabine, and mitoxantrone are described in section 7. Dose-limiting toxicities (DLTs) used for trial monitoring are defined as follows:

- **8.3.1** Any Grade 3 non-hematologic toxicity lasting >48 hours that results in >7 day delay of the subsequent treatment cycle, with the exception of febrile neutropenia or infection.
- **8.3.2** Any Grade ≥ 4 non-hematologic toxicity, with the exception of febrile neutropenia/infection unless felt to be a direct consequence of treatment-related toxicity (e.g., intenstinal infection following mucosal barrier breakdown), and with the exception of constitutional symptoms if recovery to Grade ≤ 2 within 14 days.
- **8.3.3** Lack of recovery of ANC to $\geq 500/\mu$ L and lack of self-sustained platelet count $\geq 50,000/\mu$ L by treatment day +49 with no evidence of residual leukemia.

8.4 **Duration of Follow-up**

After removal from protocol, patients will be monitored for late toxicities/complications for 1 month or until additional anti-AML therapy is given. Patients will be followed after completion of study treatment to determine disease-free survival (for patients achieving CR or CRi) as well as event-free and overall survival (for all patients), for a maximum of 5 years. Follow-up may include periodic (e.g. every 3 months) review of medical records, and, if absolutely necessary, direct contact of the study participant.

8.5 Study Endpoints

The endpoints of the phase 1 portion of this study are the determination of the MTD of decitabine in newly-diagnosed patients. Provided that the MTD is successfully determined, enrollment in the phase 2 portion of this trial at the MTD will be conducted in this population. The endpoints for the phase 2 portion of this study are (primary) MRDneg CR compared to historical controls of G-CLAM alone and (secondary) disease responses, relapse-free, and overall survival. For the primary outcome comparison, response rates will use the best response after up to 2 cycles of induction (1 with decitabine G-CLAM and 1 with G-CLAM alone).

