This protocol initially called for multiple cycles of decitabine in combination with chemotherapy: patients who failed to achieve CR without measurable residual disease (MRD), or MRDneg CR, were eligible for a 2nd cycle of decitabine + GCLAM, while those who did achieve this outcome were eligible for consolidation with decitabine + GCLA. Review of outcomes from the 4 ND patients who received on-protocol consolidation showed that 2 had delayed or absent recovery of neutrophils and platelets not related to leukemia, or morphological leukemia-free state (MLFS). Although it is difficult to interpret results from so few patients, in light of results from RR patients showing higher rates of MLFS than we would normally expect, we opt to restrict patients to a single cycle of decitabine in combination with GCLAM. Patients achieving MRDneg CR have the option of receiving GCLA consolidation (which is a standard therapy that they could receive on or off protocol), while those who do not achieve MRDneg CR will be taken off study. Because we recognize MLFS as a concern with this regimen, we will add criteria to the stopping rules to include bone marrow aplasia.

Rationale for adding a Phase 2 expansion cohort

Based on the 6 ND patients who have had their responses assessed, the combination of decitabine for 10 days and GCLAM appears to be effective. Within our first cohort of 6 patients, we had 1 DLT (a patient experienced early death), but responses in the other 5 patients showed MRDneg CR. Without an expansion cohort, we only have room to enroll another 4 patients on

Protocol 9713.00

the trial to determine the MTD or recommended Phase 2 dose (RP2D) assuming that the remaining patients have only 0 or 1 DLT. Because of these promising early results, we plan to expand our study in ND patients at the MTD/RP2D. The Phase 2 expansion includes stopping rules for both efficacy and safety.

2.0 **OBJECTIVES**

2.1 Primary Objective

- **2.1.1** Estimate the maximum tolerated dose (MTD) of decitabine when used concomitantly with G-CLAM in patients with newly diagnosed AML and highrisk MDS.
- **2.1.2** Compare, within the limits of a phase 1/2 study, the rate of complete remission without measurable residual disease (MRDneg CR) with decitabine + G-CLAM at the MTD compared to similar patients treated previously with G-CLAM alone.

2.2 Secondary Objectives

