After a achieving MRDneg CR after 1 cycle of decitabine + G-CLAM or after achieving CR/CRi after 1 cycle of decitabine + G-CLAM followed by GCLAM without decitabine, patients are eligible for consolidation therapy with G-CLA. Consolidation will not include decitabine.

- **6.8.1** The treatment is identical to the induction course but without decitabine or mitoxantrone (i.e. G-CSF, cladribine, and cytarabine, "G-CLA"), provided the patient had <Grade 3-4 non-hematologic / non-infectious toxicity during induction. If there was such toxicity, doses should be reduced as described in section 6.7.
- **6.82** Consolidation courses should start within 6 weeks of response assessment once patients have recovered to Grade ≤ 2 toxicities from the previous course of therapy.
- **6.8.3** Patients can receive up to 4 courses of consolidation therapy.
- **6.8.4** Patients can proceed to transplantation barring contraindications and if a suitable donor is available.

6.9 Supportive Therapy

- **6.9.1** All patients will be adequately hydrated and receive appropriate anti-emetics based upon NCCN guidelines [24].
- **6.9.1** Growth factors may be used according to institutional practice guidelines or the preference of the attending physician.
- **6.9.2** Antimicrobial prophylaxis should be used according to institutional practice guidelines. In case of neutropenic fever, standard diagnostic testing will be performed, and empiric antibiotic coverage will be utilized as per usual care and standard institutional practices (SCCA, UWMC, and Fred Hutch).
- **6.9.3** Transfusional support should be carried out according to institutional practice guidelines.

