14.0 STATISTICAL CONSIDERATIONS

14.1 General Considerations:

- 14.1.1 DLTs are defined in Section 8.3. Only DLTs occurring during Cycle 1 will be used to guide dose escalation.
- 14.1.2 Patients will be considered evaluable for DLT if they received at least 75% of the assigned decitabine and G-CLAM doses during Cycle 1 or if they developed a DLT. If a patient does not develop a DLT but does not receive at least 75% of treatment during Cycle 1, the patient will be considered not evaluable for DLT and will be replaced.
- 14.1.3 Maximum tolerated dose (MTD) is defined as the highest dose studied in which the incidence of DLT is <33%.

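### Section 8.3.1 does not count a qualifying Grade 3 toxicity as a DLT when no further protocol cycle follows, yet those patients stay in the DLT denominator; the date from which delay runs is also loosely defined.

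*Combined protocol and SAP*

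**What the plan says.** Section 8.3 gives three DLT criteria.

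- 8.3.1: "Any Grade 3 non-hematologic toxicity lasting >48 hours that results in >7 day delay of the subsequent treatment cycle", with febrile neutropenia and infection excepted.
- 8.3.2: any Grade 4 or higher "non-hematologic toxicity, with the exception of febrile neutropenia/infection unless felt to be a direct consequence of treatment-related toxicity", with a further exception for constitutional symptoms that recover. No next cycle is needed.
- 8.3.3: failure of neutrophil and platelet recovery "by treatment day +49 with no evidence of residual leukemia". This has a fixed date and needs no next cycle.

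Section 14.1.1 limits the window: "Only DLTs occurring during Cycle 1 will be used to guide dose escalation". Section 14.1.2 sets the denominator: "Patients will be considered evaluable for DLT if they received at least 75% of the assigned decitabine and G-CLAM doses during Cycle 1". A patient with a DLT counts as evaluable whatever the doses received. Receiving a second cycle is not a condition.

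The protocol foresees patients with no later protocol cycle. Section 6.8.4: "Patients can proceed to transplantation barring contraindications"; 6.12.2 lists transplant in remission as a reason for ending treatment, and 6.12.6 lists toxicity that prevents continuation. The 2018 update in section 1.0 notes that G-CLA consolidation may be given on or off protocol.

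On timing, 6.8.2 states: "Consolidation courses should start within 6 weeks of response assessment". Section 6.0 also gives six weeks but counts from achievement of CR/CRi. Section 6.7.1 refers to a planned start of the next cycle without defining it, and 6.6.2 gives no start date for a second induction.

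**The concern.** Criterion 8.3.1 detects a toxicity through its effect on the next cycle. If there is no next cycle, there is nothing to delay, and the text gives no other way to score the event. The patient has usually had at least 75% of Cycle 1 and so enters the DLT rate as a non-event. The ordering can then be perverse: a Grade 3 toxicity that holds up the next course for eight days is a DLT, while one that ends protocol treatment need not be.

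The DLT count decides the MTD (primary objective 2.1.1) and both Phase 2 DLT limits in 14.3. With cohorts of 6 and 12, single events matter. Section 1.0 reports 1 DLT in the first 6 newly diagnosed patients, which is the most that 14.2 allows before de-escalation. That does not show that an event was missed, but it shows how little room there is for one scored differently.

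**Working it through.** **1. The plan's own figures.** Section 14.2 gives, for 3 DLTs in 12, an 80% interval of 10% to 48% and a 90% interval of 7% to 53%. Exact (Clopper-Pearson) limits are 9.6% to 47.5% and 7.2% to 52.7%. The arithmetic is sound; the issue is what enters the count.

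**2. Which exits leave a gap.**

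| Exit after Cycle 1 | Can a prolonged Grade 3 toxicity still be a DLT? |
|---|---|
| Transplant (6.8.4, 6.12.2) | Not by 8.3.1 read literally |
| Removal for toxicity (6.12.6) | Not by 8.3.1 read literally |
| Consolidation off protocol (1.0) | Unclear: no later protocol cycle |
| Interruption over 21 days past the planned start (6.7.1) | Yes in substance: a delay over 7 days has already occurred |
| Persistent aplasia (6.6.3, 6.12.4) | The aplasia has its own criterion, 8.3.3, if its thresholds are met |
| Not in MRDneg CR | Depends on the section: off study in 1.0, second induction in 6.6.2 |

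**3. The reference date.** If delay is counted from the end of the six-week window after a marrow on Day +25 to +35, 8.3.1 is met only after Day 25 + 42 + 7 = 74 to Day 35 + 42 + 7 = 84. Criterion 8.3.3 uses Day +49. Both statements of the window are also conditional on recovery from toxicity, so the toxicity itself can move the date.

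**4. Size, by assumption.** Let p be the true DLT rate and f the fraction of all true DLTs that are missed. The counted rate is q = p(1 − f). Here f = s × m, where s is the share of DLTs that would come through 8.3.1 and m is the fraction of those in patients with no next cycle. The documents give neither. For example, f = 20% needs s = 50% and m = 40%.

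Phase 1 acceptance (at most 1 of 6, then at most 3 of 12):

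A(q) = P(0 of 6) × P(≤3 of 6) + P(1 of 6) × P(≤2 of 6)

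- q = 0.33: 0.0905 × 0.9031 + 0.2673 × 0.6870 = 0.265
- q = 0.33 × 0.8 = 0.264: 0.1590 × 0.9545 + 0.3421 × 0.8078 = 0.428

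Phase 2 includes patients treated at the RP2D in Phase 1 (14.3), so for Level 1 the first 12 of the 19 stage 1 patients have already passed the Phase 1 rule. With a, b, c and d DLTs in successive groups of 6, 6, 7 and 22, the joint pass probability is

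J(q) = P(a ≤ 1, a+b ≤ 3, a+b+c ≤ 6, a+b+c+d ≤ 13).

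This treats suspension at 7 of 19 as a stop. Exact binomial sums give:

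| Missed, f | Counted rate, true 33% | A | J | J/A | Counted rate, true 40% | A | J |
|---|---|---|---|---|---|---|---|
| 0 | 33.0% | 27% | 19% | 72% | 40% | 14% | 6% |
| 5% | 31.4% | 30% | 24% | 78% | 38% | 17% | 9% |
| 10% | 29.7% | 34% | 29% | 84% | 36% | 21% | 12% |
| 20% | 26.4% | 43% | 39% | 92% | 32% | 29% | 22% |

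J/A is the chance of passing both Phase 2 limits once Phase 1 has been passed.

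**The case against.** The case against is substantial, and much of it stands.

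- A reader might infer that the DLT rate is in fact under-counted. The documents do not show that. The exposure is confined to Grade 3 non-hematologic, non-infectious events, since 8.3.2 and 8.3.3 apply with or without a next cycle. No count of affected patients is given. Section 1.0 mentions 4 newly diagnosed patients with on-protocol consolidation and 6 with response assessed, 5 of them in MRDneg CR. These may not be the same group, and the figures predate the update.
- A reader might add everyone not in MRDneg CR, because section 1.0 says "while those who do not achieve MRDneg CR will be taken off study". Sections 6.6.2, 6.8 and 8.5 instead provide for a second induction. This is a contradiction to resolve, not evidence of a larger affected group.
- A reader might say the delay cannot be measured. That is too strong: consolidation has a six-week outer limit. The date is loosely defined, and this ambiguity alone could push scoring in either direction.
- A reader might treat all 41 Phase 2 patients as new and find that the chance of passing both limits goes from 40% to 72% at f = 20%. That ignores the carry-over from Phase 1; 19% against 39% is the relevant joint figure.
- An investigator may sensibly score removal for unresolved Grade 3 toxicity as an indefinite delay. The text does not say so.

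What is left is a scoring rule that, applied as written, can err only towards fewer DLTs in patients with no next cycle.

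**Conclusion.** The point holds in limited form. Section 8.3.1 makes a Grade 3 DLT depend on a later protocol cycle, 14.1.2 keeps patients without one in the denominator, and no passage reconciles the two. Any bias from this source is downward and loosens the Phase 1 rule and both Phase 2 limits. Its size cannot be taken from the documents. The range from 27% to 30–43% for Phase 1 acceptance, and from 19% to 24–39% for the joint pass, rests on an assumed loss of 5% to 20% of true DLTs at a true rate of 33%, on independent patients, and on Level 1 being the dose carried forward. If few DLTs would arise through 8.3.1, or few such patients lack a next cycle, the effect is small. The undefined reference date is a separate weakness with no fixed direction.

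**What to change.** Amend section 8.3.1 in three respects:

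1. A qualifying Grade 3 toxicity that prevents the next protocol cycle is scored in the same way as one that delays it.
2. State how 8.3.1 is scored when there is no next protocol cycle for another reason, such as transplant or off-protocol consolidation. If such patients are to be non-evaluable, 14.1.2 must say so and provide for replacement.
3. Define once the date from which delay is counted, for both consolidation and second induction.

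Say also whether the amended rule applies to patients already treated, since Phase 1 patients at the RP2D are carried into Phase 2.

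Reconcile three sets of passages: 1.0 with 6.6.2 on second induction; 6.0 with 6.8.2 on the start of the six-week window; and the recovery grade needed for further treatment, which is below Grade 2 in 6.6.2 and 6.7.1 but Grade 2 or lower in 6.0 and 6.8.2. The clinical threshold is for the sponsor to set.

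The cost is a few sentences of protocol text. Start and stop dates of non-hematologic Grade 3 events are already recorded (11.3, 11.4). A rule that depended on recovery to a lower grade might need an extra date, because section 11 does not call for Grade 2 events to be recorded routinely. The downside is that a few more DLTs may be counted, making de-escalation or suspension somewhat more likely.
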